**11/06/2024**

## **1. Study protocol**

### **1.1. Expected duration of participation of individuals**

All participants (n=216) will be invited to a 45-minute visit (test). A second visit will be organized for the 60 patients randomly selected for a 15-day retest.

The maximum duration of participation is therefore 15 days.

### **1.2. Description of the acts performed on the persons (description of each visit)**

**Visit 1 (Test):** Patients will be seen by the local investigator/examiner who will assess the eligibility of patients according to the inclusion and non-inclusion criteria described above.

#### **HD group**

- Clinical examination performed to confirm the diagnosis of HD (Schiff score on the air jet test  $\geq 1$ );
- Air jet test: determination of the Schiff score (score  $\geq 1$ ) and the EVA score;
- Self-administration of DHEQ-fr, GOHAI and OHIP questionnaires.

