#### **Control group**

- Clinical examination performed to confirm the absence of HD;
- Self-administration of DHEQ-fr, GOHAI and OHIP questionnaires.

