#### **Visit 2 (Retest)**

#### **HD Group and Control**

- Self-administration of DHEQ-fr questionnaires.

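### As section 1.2 lists the acts, only HD patients at Visit 1 meet an air jet test before the DHEQ-fr, so the HD-control difference and HD test-retest agreement are open to a possible procedure effect

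*Protocol*

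**What the plan says.** Protocol section 1.2 has the examiner assess eligibility at Visit 1 and then lists the acts by group.

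- **HD group, Visit 1.** Three bullets: "Clinical examination performed to confirm the diagnosis of HD (Schiff score on the air jet test" (a score of at least 1); then "Air jet test: determination of the Schiff score (score $\geq 1$ ) and the EVA score"; then "Self-administration of DHEQ-fr, GOHAI and OHIP questionnaires".
- **Control group, Visit 1.** Two bullets: "Clinical examination performed to confirm the absence of HD", then the same questionnaires. No air jet test is named, and the means of ruling out HD is not given.
- **Visit 2, both groups.** One bullet: "Self-administration of DHEQ-fr questionnaires".

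Section 1.1 gives 216 participants at Visit 1 and says that "A second visit will be organized for the 60 patients randomly selected for a 15-day retest". It does not say how many of the 60 are HD patients.

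The Visit 1 scores feed two analyses in section 2.1.2. One is the HD-control comparison (t-test or Mann-Whitney test, reported as an effect size with a 95% confidence interval). The other is test-retest agreement on the overall score (paired t-test, correlation, Lin's coefficient, Bland-Altman plot).

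**The concern.** The DHEQ-fr asks about the impact of tooth sensitivity. As listed, an HD patient has sensitivity provoked and scored shortly before answering. A control answers after an examination with no such stimulus named. At the retest, nobody has a procedure beforehand.

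If the stimulus alters the answers, the alteration enters the HD-control difference in full. Adjustment cannot take it out: section 2.1.1 adjusts for factors unbalanced between groups, but as listed the air jet coincides exactly with group. For HD patients in the retest sample, the same alteration appears as a mean difference between visits. Section 2.1.2 defines reproducibility by the stability of the person's condition and does not ask for equal conditions of administration.

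Both analyses are central to validating the questionnaire.

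**Working it through.** The protocol states no figure that can be reproduced here. The first step sets the lists side by side; the second is an illustration under assumptions.

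**Step 1: conditions before the DHEQ-fr, as listed in section 1.2**

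| | Examination | Air jet test | Then DHEQ-fr |
|---|---|---|---|
| HD, Visit 1 | yes | yes, with Schiff and EVA scores | yes |
| Control, Visit 1 | yes | none named | yes |
| HD and control, Visit 2 | none listed | none listed | yes |

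The order is more than layout. Eligibility is assessed at Visit 1 and the HD diagnosis rests on the Schiff score from the air jet test, so a site that confirms eligibility first will give the questionnaires afterwards.

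**Step 2: what a shift would do**

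From the protocol: 60 retest pairs, two-sided 5% level. Assumed: 30 HD and 30 control pairs, all pooled (section 2.1.2 names no analysis by group); within-group SD of 1 at each visit; within-group test-retest correlation r = 0.85; a uniform shift of u SD in HD patients at Visit 1 only; a true HD-control difference D = 0.5 SD, needed only for pooled Lin.

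- HD-control difference at Visit 1: D + u, so it moves by exactly u.
- Pooled mean change between visits: 0.5u.
- SD of pooled differences: sqrt(2(1 − r) + 0.25u²).
- Noncentrality of the paired t-test (59 degrees of freedom): 0.5u × sqrt(60) / SD of differences.
- Pooled Lin: 2C / (V1 + V2 + 0.25u²), with C = r + 0.25(D + u)D, V1 = 1 + 0.25(D + u)², V2 = 1 + 0.25D².

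For u = 0.2, the SD of differences is sqrt(0.30 + 0.01) = 0.557 and the noncentrality is 0.1 × 7.746 / 0.557 = 1.39, so the test rejects about 28% of the time. Pooled Lin is 2 × 0.9375 / (1.1225 + 1.0625 + 0.01) = 0.854.

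| Shift u (SD) | HD-control difference if truly 0.5 | Pooled paired t-test rejects | Pooled Lin |
|---|---|---|---|
| 0 | 0.5 | 5% | 0.859 |
| 0.1 | 0.6 | 11% | 0.858 |
| 0.2 | 0.7 | 28% | 0.854 |
| 0.3 | 0.8 | 52% | 0.846 |
| 0.5 | 1.0 | 89% | 0.821 |

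With r = 0.80 the rejection rates become 9%, 22%, 42% and 80%.

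Up to 0.3 SD, pooled Lin falls by at most 0.859 − 0.846 = 0.013. A modest shift would thus act in full on the HD-control difference, hardly touch pooled agreement, and often escape the pooled paired test. Among HD patients alone, Lin is r/(1 + u²/2), which gives 0.846, 0.833, 0.813 and 0.756, so agreement reported by group is more sensitive to it.

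**The case against.** Several points on the other side have force.

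- **A list is not a timetable.** Section 1.2 describes acts, uses no word such as then or after, and mentions the air jet test in two HD bullets, which does not suit a strict sequence. This stands: the order is plausible, not proven. But an unfixed order across three centres is also a weakness, and the same sentence would cure it.
- **Controls may be air-tested too.** HD is defined through the air jet test, so ruling it out may involve one. The documents do not settle this. If controls are tested, much of the asymmetry between groups goes, but the contrast between visits remains.
- **No effect is shown.** This stands. A reader might infer that known-groups validity is overstated and reproducibility understated. The protocol gives no effect, direction or size, so neither follows. Nor can an effect of learning the diagnosis be assumed to vanish by the retest, since a patient told at Visit 1 would still know 15 days later.
- **A shift can be told from noise.** A reader might infer that a shift could not be separated from unreliability. That goes too far: a uniform shift leaves the correlation within HD patients unchanged, lowers Lin and appears as Bland-Altman bias. What these statistics cannot do is say whether the procedure or the instrument caused it.
- **HD-only rejection rates are not the plan's.** Testing 30 HD pairs alone would give about 16%, 49%, 83% and more than 99% at r = 0.85. The plan names no such test, so the pooled figures are the relevant ones.

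**Conclusion.** The point holds as a risk of bias that the protocol leaves open, not as a demonstrated bias. As listed, the DHEQ-fr is completed under conditions that differ between groups at Visit 1 and, for HD patients, between visits, and nothing in the document fixes another order.

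Confidence is high that the listed conditions differ and that the order is uncontrolled. Whether scores actually move is unknown. Any shift would pass in full into the HD-control difference. The detection rates of 11% to 89% for shifts of 0.1 to 0.5 SD rest on an assumed r of 0.85, an assumed even split of the 60, and pooling. The change is worth making because it is cheap and removes a possible bias that adjustment cannot.

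**What to change.** In section 1.2, state that DHEQ-fr, GOHAI and OHIP are completed first at Visit 1 in both groups, before the examination and the air jet test, so that Visit 1 matches Visit 2. Exclude the questionnaires of people then found ineligible. In section 2.1.2, add test-retest agreement reported separately for HD patients. If recruitment has begun, record the order used for each participant.

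No extra visit or procedure is needed. The downside is that some people will complete questionnaires that are then discarded; the protocol gives no basis for estimating how many.

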#### **Control group**

- Clinical examination performed to confirm the absence of HD;
- Self-administration of DHEQ-fr, GOHAI and OHIP questionnaires.

#### **Visit 2 (Retest)**

#### **HD Group and Control**

- Self-administration of DHEQ-fr questionnaires.

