### **1.3. Description of the general logistical organization of the trial**

Patient recruitment will be done in three centers (Odontology Department of Clermont-Ferrand, Bordeaux and Lyon), after informing all practitioners and practicing students about the present study and the need to refer patients with HD symptoms to the local investigator.

A local co-investigator/examiner will conduct visits to all patients at the investigator center in which they practice; His senior will ensure methodological and administrative supervision of the Investigator Center in which he works.

The principal investigator and the biostatistician will take charge of the data analysis.

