## **2. Statistical analysis plan**

### **2.1. Data Analysis Method**

### 2.1.1. General

The statistical analysis will be carried out with the Stata software (version 15, StataCorp, College Station), considering a first-kind bilateral risk of error of 5%.

The sample will be described by associated numbers and percentages for categorical variables and by mean and standard deviation or median and interquartile range for quantitative variables, with respect to their statistical distribution. Normality will be studied by the Shapiro-Wilk test and/or histogram. Graphical representations will be associated with the analyses as much as possible.

Patients will be described and compared between groups at baseline according to the following variables: compliance with eligibility criteria, epidemiological characteristics and clinical characteristics.

A description of the deviations from the protocol, the patients distributed according to these deviations and the causes of abandonment will also be carried out.

The initial comparability of the two arms will be assessed on the main characteristics of the participants and potential factors associated with the primary outcome. Any difference between the two groups on one of these characteristics will be determined according to clinical considerations and not just statistical ones. Comparisons between groups will be made systematically (1) without adjustment and (2) by adjusting for factors whose distribution could be unbalanced between groups despite the matching.

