### 2.1.2. Statistical analyses

The validation of the DHEQ-fr will consider the study of psychometric properties according to the following plan:

The measure of **acceptability** will be based on the calculation of missing data at the item level and for the overall score; the scale will be considered applicable if the conditions of use show that the cost of implementation is modest, that the acceptability by patients and the medical community is high, and that the time to pass is low.

The **fidelity** of the instrument will be assessed according to two criteria:

- o *Internal consistency* will be assessed by calculating the Cronbach alpha coefficient (Kuder-Richardson  $\alpha_k$ ) and will be studied against the usual recommendations described as follows:  $\alpha_k \geq 0.9$  excellent;  $0.9 > \alpha_k \geq 0.8$  correct;  $0.8 > \alpha_k \geq 0.7$  acceptable;  $0.7 > \alpha_k \geq 0.6$  moderate;  $0.6 > \alpha_k \geq 0.5$  low; and  $0.5 < \alpha_k$  not acceptable.
- o *Test-retest reproducibility*, the ability to produce comparable responses when the measure is repeated while the individual's condition remains stable, will be assessed by calculating the intensity of agreement (for items of a quantitative nature: Lin's coefficient of agreement and for items of a categorical nature: agreement rate: for each item, percentage of identical responses during the test and retest and the Kappa coefficient of agreement (denoted  $k$ ) compared to the following recommendations: no agreement ( $k < 0.2$ ), low agreement ( $k$  0.2 to 0.4), moderate agreement ( $k$  0.4 to 0.6), substantial agreement ( $k$  0.6 to 0.8), or excellent agreement ( $k > 0.8$ ). The overall score will be compared in a test-retest situation by the paired

Student's test in addition to the correlation coefficient (Pearson or Spearman with regard to the statistical distribution) and the Lin concordance coefficient. A graphical representation of Bland and Altman will complete these analyses.

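### The retest analysis presumes a stable condition, but the DHEQ-fr is the only act listed at Visit 2, so real change cannot be told from inconsistent answering

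*Protocol*

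**What the plan says.** Protocol section 2.1.2 defines test-retest reproducibility as "the ability to produce comparable responses when the measure is repeated while the individual's condition remains stable". It plans Lin's coefficient, the agreement rate and kappa at item level. For the overall score it plans a paired Student's test, a correlation coefficient, Lin's coefficient and a Bland-Altman plot.

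Section 1.1 sets the sample and the interval: "A second visit will be organized for the 60 patients randomly selected for a 15-day retest".

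Section 1.2 gives the content of each visit:

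- Visit 1, HD group: a clinical examination confirming the diagnosis, "Air jet test: determination of the Schiff score" and of the EVA score, and the DHEQ-fr, GOHAI and OHIP.
- Visit 1, control group: "Clinical examination performed to confirm the absence of HD", and the same questionnaires.
- Visit 2, both groups: "Self-administration of DHEQ-fr questionnaires", and nothing else.

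**The concern.** Stability is part of the protocol's own definition of what it sets out to measure, but nothing listed at Visit 2 bears on it. The DHEQ-fr is the instrument under test, so a change in its score cannot also serve as independent evidence that the patient changed.

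Change within 15 days is plausible. Section 1.3 recruits in odontology departments, "after informing all practitioners and practicing students about the present study and the need to refer patients with HD symptoms" to the local investigator, so dental care between the visits is possible.

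Each planned statistic can show disagreement; none can say whether it is real change or inconsistent answering. If the retest coefficient came out lower than hoped, the team could not tell whether the questionnaire or the patients were responsible. Care given in the recruiting departments might be traced in their records, but a change in symptoms that nobody asked about could not be recovered by any later analysis plan.

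**Working it through.** **Text check.** Two other places in the protocol might have closed the gap.

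- Section 2.1.3 compares the test and retest samples on socio-demographic and clinical characteristics. No clinical characteristic is listed at Visit 2, so this shows who was retested, not whether each of them stayed stable.
- Section 2.1.1 plans "A description of the deviations from the protocol". That would reveal interim care only if care is barred, and it would not reveal a change in symptoms.

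**Size.** The protocol states no expected retest coefficient, so there is no figure to reproduce. What follows is an illustration. Only n = 60 and the two-sided 5% level come from the protocol; everything else is assumed.

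Assumptions: within-group SD 1; within-group Lin 0.80; a share p of the retested are HD patients (the split is not stated; p = 0.5 means 30 and 30); a share q of HD patients change by δ SD in balanced directions; controls are stable; HD and control means differ by D SD.

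Lin in all retested = 2[0.80 + p(1−p)D²] / [2 + 2p(1−p)D² + pqδ²]

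With D = 0, change in one direction gives the same value. Results for D = 0:

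| Change among HD patients | All 60 (p = 0.5) | HD patients alone (p = 1) |
|---|---|---|
| 10% by 0.5 SD | 1.6/2.0125 = 0.795 | 1.6/2.025 = 0.790 |
| 20% by 1 SD | 1.6/2.10 = 0.762 | 1.6/2.20 = 0.727 |
| 30% by 1 SD | 1.6/2.15 = 0.744 | 1.6/2.30 = 0.696 |

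- *Split.* At 20% by 1 SD, the value in all 60 is 0.774 with 20 HD patients and 0.750 with 40.
- *Group difference.* With D = 1 and p = 0.5, the coefficient without change is 2.1/2.5 = 0.840. At 20% by 1 SD it appears as 2.1/2.6 = 0.808 if change is balanced and 0.800 if all improve.
- *What a large fall needs.* For all 60 to show 0.727 or 0.696, 40% or 60% of the HD patients would have to change by 1 SD.

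**Would the paired t-test warn?** Take D = 0, p = 0.5, and HD patients all changing by 1 SD in the same direction. The overall share changing is f = 0.5q, the mean difference is f, and the SD of the differences is √[2(1−0.80) + f(1−f)]. At q = 0.2, f = 0.10, the SD is √(0.40 + 0.09) = 0.70, and the noncentrality is 0.10/(0.70/√60) = 1.11. Power from the noncentral t distribution is 0.19. The same calculation gives 0.35 at q = 0.3, 0.53 at q = 0.4 and 0.83 at q = 0.6. If change is balanced, rejection is at most about 5%.

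**Would a stable subset help?** Simulation (20,000 runs, 30 + 30, 20% of HD patients changing by 1 SD in balanced directions, D = 0) gives these mean Lin values; finite samples put them slightly below the formula:

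- all 60: 0.75
- HD patients alone: 0.71
- the 54 stable patients, if self-report is perfect: 0.79
- about 50 patients, if self-report detects 70% of changers and wrongly flags 10% of stable patients: 0.78

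**The case against.** The case against has real weight.

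- *Omission, not contradiction.* Section 2.1.2 gives the general definition and does not promise to verify stability. A 15-day interval is itself a way of making stability plausible. This is right, and the point is accordingly one of design. Still, a short interval makes stability likely without showing it.
- *Unseen text.* The eligibility criteria are not in the text available and may restrict care. Section 1.2 is headed "Description of the acts performed on the persons (description of each visit"), so it lists acts, and the retest form could hold questions that are not acts. Both limits stand. A criterion applied at entry, however, would not record whether symptoms changed during the 15 days.
- *Small and assumed effect.* At 20% by 1 SD, the fall from 0.80 to 0.76 lies well inside the sampling interval for 60 patients (0.69 to 0.88). The HD-only values describe a coefficient that section 2.1.2 does not explicitly plan. Both remarks are fair.
- *The paired t-test often does signal larger one-way change.* True: 0.35 to 0.83 for 30% to 60% of HD patients. It seldom warns at the 20% case or when change is balanced. When it does reject, it still does not say whether the patients or their answering changed. The same holds for the Bland-Altman plot, which would show large individual shifts but not their cause.
- *Conservative bias and modest gain.* Real change would not make an unreliable questionnaire look reliable, and imperfect self-report recovers only part of the loss (0.75 to 0.78). Choosing self-declared stable patients may also favour consistent responders. This is why all 60 should remain the headline.

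**Conclusion.** The concern holds. The protocol defines reproducibility for a stable condition, and nothing listed at Visit 2 can show whether the condition was stable. The likely consequence is a modest understatement of reproducibility, mainly in the HD group. Under the assumed values it ranges from negligible (0.80 appearing as 0.795) to a fall to 0.76 or 0.74 in all 60 retested patients. These sizes rest on an assumed coefficient, split and share of changers, none of which the protocol gives. Confidence is medium, because the eligibility criteria and the retest form are not available. The change is worth making because it is cheap and the missing information cannot be collected afterwards.

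**What to change.** Add two self-report questions to the Visit 2 form in both groups:

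1. Tooth sensitivity since Visit 1: same, better or worse.
2. Any dental care since Visit 1: yes or no.

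Keep the retest coefficients in all 60 patients as planned and as the headline. Pre-specify the same coefficients in patients who report no change and no care, reported alongside, with the number set aside in each group.

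The cost is two items on an existing form and one pre-stated secondary analysis. Precision in the subset is only slightly lower. By Fisher's z with standard error 1/√(n−3), a coefficient of 0.80 (z = 1.099) has a 95% interval of 0.69 to 0.88 with 60 patients (standard error 0.132). With 54 patients, that is with 6 of 30 HD patients set aside, it is 0.68 to 0.88 (standard error 0.140). The report should say that self-reported stability is imperfect and may raise agreement by selecting consistent responders.

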### **1.3. Description of the general logistical organization of the trial**

Patient recruitment will be done in three centers (Odontology Department of Clermont-Ferrand, Bordeaux and Lyon), after informing all practitioners and practicing students about the present study and the need to refer patients with HD symptoms to the local investigator.

A local co-investigator/examiner will conduct visits to all patients at the investigator center in which they practice; His senior will ensure methodological and administrative supervision of the Investigator Center in which he works.

The principal investigator and the biostatistician will take charge of the data analysis.

### **1.4. Study samples and biological analyses**

No samples will be taken during this study. No biological analysis will be performed during this study.

## **2. Statistical analysis plan**

### **2.1. Data Analysis Method**

### 2.1.1. General

The statistical analysis will be carried out with the Stata software (version 15, StataCorp, College Station), considering a first-kind bilateral risk of error of 5%.

The sample will be described by associated numbers and percentages for categorical variables and by mean and standard deviation or median and interquartile range for quantitative variables, with respect to their statistical distribution. Normality will be studied by the Shapiro-Wilk test and/or histogram. Graphical representations will be associated with the analyses as much as possible.

Patients will be described and compared between groups at baseline according to the following variables: compliance with eligibility criteria, epidemiological characteristics and clinical characteristics.

A description of the deviations from the protocol, the patients distributed according to these deviations and the causes of abandonment will also be carried out.

The initial comparability of the two arms will be assessed on the main characteristics of the participants and potential factors associated with the primary outcome. Any difference between the two groups on one of these characteristics will be determined according to clinical considerations and not just statistical ones. Comparisons between groups will be made systematically (1) without adjustment and (2) by adjusting for factors whose distribution could be unbalanced between groups despite the matching.

